#### Randomisation to 18 month follow up;

**Primary Aim:** We aim to carry out a pragmatic trial that will inform policy makers, commissioners of services and professionals about the potential of MST in a UK context, investigating whether the provision of MST could reduce the incidence of out of home placements for young people at risk of being removed from their homes because of antisocial behaviour, severe mental health problems, educational problems or unmet need. The trial will take referrals of families with an adolescent with severe antisocial behaviour problems who is considered to be at risk of custodial or other forms of out of home care. The trial will answer the question of whether MST can contribute to significantly reducing the rate of out of home placement

**Secondary Aim:** We will investigate whether MST is associated with (a) decrease in antisocial behaviour, (b) increase in young person's well-being, (c) improved educational outcomes and (d) improved family functioning. Moreover, we aim to establish the cost of MST relative to management as usual, and the cost-effectiveness of providing this intensive form of intervention against the background of costs incurred in the 18 months period following randomisation.

The immediate objectives of the trial are: (1) to confirm recruitment of ten MST service providers and agree on an acceptable protocol for randomisation of cases (month 3); (2) to recruit and train outcome assessors (OAs) to a predetermined level of reliability (month 4); (3) to identify a representative clinical sample of 700 young people to be recruited from ten sites (month 21); (4) to randomise 350 cases to MST and 350 to MAU (month 21 – this figure allows for a significant number who may not consent to enter the trial); (5) to assess outcome of randomised cases at 6, 12, 18, 24,30 and 36 months post recruitment (month 39); (6) to estimate the total social, health, educational and criminal justice cost of interventions at 18 months post-randomisation (month 42); (7) to identify the key cost and outcome drivers and the value for money of the treatments at 18 months (month 44) and (8) to analyse data, write reports and prepare papers for publication in peer reviewed journals 4 years after the commencement of the trial (month 48).

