MST. This is a potential source of bias and could, if criteria interact with suitability, generate builtin between site differences. We intend to use the expertise that we have built up both in London and in Cambridge to work with each multi-agency panel and create a homogenous recruitment protocol for the panels to work to which would also be consistent with the eligibility criteria for the trial. We are currently in discussion with the sites regarding this protocol. The key components of such a protocol would include a standard referral form including information pertaining to inclusion and exclusion criteria which will form the first screen to the trial focusing on establishing severity and chronicity. Following the acceptance of the referral by the Panel, a standard initial letter in the first language of the family from the multi-agency panel will be sent to parents and separately to the young person if s/he is 16, informing them about the trial, standard explanatory visit and a standard consenting procedure. Recruitment begins with this letter which would be sent to all those identified by a panel to be probably suitable for MST. The letter from the panel (or the MST referral team) would invite participation, and informs families and the young person that someone from the MST team (preferably the MST supervisor) will contact them unless they do not wish to participate in the trial. The letter would include material in age and culturally appropriate language in the form of a leaflet for both the parents and the young person explaining the trial and what involvement in the trial would mean at that particular site. Information sheets have been constructed and designed with input from young people and their parents/carers who have used MST in order to make them as useful and accessible as possible. Separate, specifically adapted sheets are included for different age ranges; one for children aged 11-15 and one for young people aged 16-17, containing the same information as the parent/carer sheet but in age-appropriate language. Information sheets have been constructed and designed with input from young people and their parents/carers who have used MST in order to make them as useful and accessible as possible. The MST supervisor and therapist will be on hand at consent meetings to explain anything in the information sheets and consent forms that is unclear. After a brief period of time (1-2 weeks) the family would be contacted by a member of the MST team to explain in person what participation might involve and to arrange an appointment. This is the second stage of the multiple gating procedure and the MST worker might identify exclusion criteria at this stage (e.g. risk of possible injury to worker, incompatible agency involvement, severe substance dependence). Consent forms would not be signed at this appointment because experience has shown that actual take-up of treatment increases dramatically and early dropouts are reduced if the family feels they have been given adequate time to consider their participation. Unless the family expresses a decision not to participate at the time of the visit, a phone contact would be made by the OA no less than 3 days after MST and the trial have been explained to families or within 7 days should the family wish for more time to think about the trial. This would be the time for reviewing the consent form and if signed. completing pre-randomisation questionnaires and measures. At this second visit, the final evaluation for eligibility is made (screen 3). When all the instruments have been completed and trial eligibility confirmed, the OA makes a call to the trial centre to obtain the allocation.

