situation would change, not wishing anybody to work in the family home or planning to move out of the borough soon. 88% of those consenting and undertaking baseline assessment will be expected to participate in the trial with 12% excluded because they did not meet criteria. Thus we assume no more than about a third of those referred will participate but that 55% of appropriate referrals meeting criteria will participate with approximately 40% of those referred being excluded as failing to meet criteria. It should be noted that although these assumptions mean that only a relatively small number of those referred will be included in the trial, data indicates that immediate dropout from treatment for severe conduct problems is in any case very high (Kazdin & Wasser, 2000). Thus, those receiving MST are likely to be a much higher proportion of those adolescents who, in the real world would be willing to engage with therapeutic services for treatment. To recruit 700 adolescents who are considered at severe risk of out of home placement we would expect approximately 2,117 to be referred to the MST multi-agency panel. This means about 200-225 families referred to each site over the study period. It should be remembered that these may be conservative assumptions that reflect the severe forensic problems that characterise the BCT sample.

**Randomistion:** Eligible consenting participants will be randomised on a 1:1 basis by the Clinical Trials Unit at UCL using a secure, automated 24 hour telephone randomisation service that will ensure allocation concealment. A computer-generated adaptive minimisation algorithm that incorporates a random element will be used with the following stratification factors: treatment centre, gender, age (11-14, 15-17), age at onset of severe conduct problems (2-11, 11+), number of past convictions ( $\leq 2/\geq 3$ ). These strata have been selected because previous research (see Background) has shown that younger age of onset and greater number of previous convictions are associated with poorer prognosis and there is insufficient evidence concerning gender mix, particularly in the older age groups, to ensure that simple randomisation would generate comparable groups. Minimisation should ensure that there will be an even distribution of adolescents across the two arms of the trial.

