#### **Measures:**

Follow-up assessments will be at 6, 12, 18, 24, 36 and 48 months post randomisation, with primary outcomes collected until 5 years post randomisation.

(a) Principles of measurement: The measures will be made across multiple domains (specific to criminal behaviour, family function, user satisfaction, comorbid problems and economic costs), using multiple methods (interviews, questionnaires, records), and multiple sources (adolescent, parent, teachers) to maximise the clinical validity of the outcome assessments and minimise bias arising from any single source of information. Where possible, measures will be made by individuals blind to treatment allocation. Many of the measures have been selected because they are part of an ambitious project under-way in the Parenting Academy (Scott, Dabbs et al.) with a range of samples, including with a large sample of looked after children, which will provide UK norms against which the current sample may be compared.

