Data on MST contacts will be collected directly from pilot schemes to avoid participants revealing their group allocation to the research assessors. Data on the use of all other services will be collected in interview using the Child and Adolescent Service Use Schedule (CA-SUS), developed and successfully employed by the applicants in previous evaluations with young people with complex mental health and social care needs (Barrett, Byford, Chitsabesan, & Kenning, 2006; Byford et al., 2007; Clark et al., 2005; Harrington et al., 2000). The CA-SUS will be adapted to the current population through review of the literature and pilot testing, to ensure comprehensive coverage and face validity.

The cost of the trial interventions will be calculated through a detailed micro-costing (or bottomup) approach using standard costing methodology (Beecham & Knapp, 1992; Drummond, O'Brien, & Stoddart 1997), which will involve estimation of indirect time spent on individual cases, including preparation, meetings, telephone calls and supervision, as well as detailed recording of direct face-to-face contact. Unit costs will be calculated using data on salaries, employer on-costs (National Insurance and superannuation), conditions of service and appropriate administrative, managerial and capital overheads (Curtis, 2007). National unit costs will be applied to all other resources used by participants, where available (e.g. British Medical Association & Royal Pharmaceutical Society of Great Britain, 2007; Curtis, 2007; Department of Health, 2007; HM Prison Service, 2007; Home Office, 2005).

(d) *The MST Adherence Measures:* The MST team in South Carolina have developed a form measuring MST adherence derived from the nine principles, to be completed by the parent(s). This will be used to measure adherence in the trial. We understand that these data are likely to be available to the research team. It would seem costly and wasteful to undertake a separate coding for adherence which would in any case need to be validated by the originators of the treatment.

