#### Design and Methodology (Annual follow up from 2-5 years)

The annual follow-up period from 2 years post randomisation will extend the primary outcome window to 60 months and carry out an evaluation of a broadened range of outcomes of both MST and MAU to 48 months. We will conduct annual full-blind outcome evaluations up to 48 months post-randomisation. Data on service use will be collected using the Child and Adolescent Service Use Schedule (CA-SUS) and Children & Young People, Resources, Evaluation and Systems Schedule (CYPRESS) (Pilling et al., 2012). Data will be used to characterise services and provide currently lacking information on transitions from child to adult services, identifying correlates of a smooth transition (continuation of appropriate services across the 18-year barrier) and testing the hypothesis that transition is important to relatively better outcomes. A a semi-structured interview will explore young people's and primary caregivers' views of change or the absence of change in key outcome domains and the families experiences of services and of the transition between services.

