3. How much control do you think you have over how that future will unfold? (prompt: what abilities do you think you will be drawing on?)

4. Do you think there is help you can draw on to help you as you go through the process of becoming an adult? (prompts: parents, peers, institutions)

While the qualitative arm has clearly been shaped by the quantitative component, it will also have its own integrity. The interviewer will start with the questions on the schedule, but their primary task will be to explore in detail the personal lived experience of the participant within the broad parameters of the domains.

The young people and caregivers will be interviewed separately. They will be interviewed about their experiences of (a) good and bad outcomes across the domains listed above, (b) engagement and contact with services and difficulties encountered, particularly in relation to transition from child to adult services. We will work with MAC-UK young advisors to develop the best format for data acquisition from this group of purposively sampled adolescents. We will also sample 36 clinicians who will be interviewed in the first year of the study in relation to barriers they encountered in implementation and delivery of services. The transcribed interviews will undergo a synthesis of IPA and framework analysis ([name] et all.,2009; Ritchie, Spencer,1994)),

the results of which can then be examined alongside the results of the quantitative analysis of secondary outcome

**Trial management:** There will be 3 Centres: London (UCL and IoP), Leeds and Cambridge. A trial manager at postdoctoral level will be appointed at the UCL site. There will be 4 RAs based at the three research sites (London, with one RA at UCL and one at Iop, Cambridge and Leeds). London will cover 4 MST sites and the others 5 each. They will work semi-independently from others to ensure blindness in coding and interviewing. They will be able to support each other in doing assessments in order to maximise the possibility of blindness (also enforced by instruction to families) so that site A will have an OA from team 1 and someone doing qualitative interview with the same family from Team 2. Economic analysis will be based at the IoP and mediational analysis in Cambridge and the IoP. OAs and the trial co-ordinator will meet weekly across sites by telephone conference. There will be a trial advisory committee including international experts from both Europe and North America.

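### The outcome assessor telephones for the allocation, and no rule keeps that assessor from following up the same family, which undercuts the protocol's own blinding

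*Protocol*

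**What the plan says.** **Who learns the arm.** Methods of recruitment and consent describes the last step before treatment. The OA visits, reviews consent, completes the baseline measures and makes the final eligibility check. Then "the OA makes a call to the trial centre to obtain the allocation". The abbreviation is explained in the objectives of the Trial Summary: "to recruit and train outcome assessors (OAs) to a predetermined level of reliability".

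**How allocation is generated.** The randomisation paragraph has the trials unit allocate "using a secure, automated 24 hour telephone randomisation service that will ensure allocation concealment".

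**What is promised about blinding.**
- Measures, principles of measurement: "Where possible, measures will be made by individuals blind to treatment allocation".
- Measures, economic evaluation: MST contact data come straight from the pilot schemes "to avoid participants revealing their group allocation to the research assessors". The years 2 to 5 section repeats this arrangement.
- Design and Methodology (Annual follow up from 2-5 years): "We will conduct annual full-blind outcome evaluations up to 48 months".
- Trial management: "There will be 4 RAs based at the three research sites". They are to work semi-independently so that coding and interviewing stay blind, and families are to be instructed accordingly. On cross-cover: "They will be able to support each other in doing assessments in order to maximise the possibility of blindness".

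**The concern.** Families and therapists in this trial necessarily know the treatment. Keeping the assessor unaware of the arm is therefore one of the few protections left against biased measurement, and the protocol spends effort on it by routing contact data around the assessors, instructing families and organising the research assistants. The allocation call works against all of this, because it tells the arm to the person whose role is to assess outcomes. For that family, withholding MST contact data from the same assessor then serves no purpose.

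At stake is detection bias in outcomes where the assessor's questioning, probing or judgement shapes the recorded value. Once an assessor knows the arm, this cannot be reversed or corrected in the analysis. The remedy therefore belongs in the trial procedures and not in a later analysis document.

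**Working it through.** No formula applies: the point depends on no power, rate or effect size, and the protocol gives no figure to reproduce. The check sets the texts on randomisation, blinding and staffing side by side.

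1. **Does an outcome assessor learn the arm?** Yes, as written. The call is stated as a definite step, its purpose is to obtain the allocation, and the caller is the OA. So, for each randomised family, one OA knows the arm from the day of randomisation.

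2. **Does the automated telephone service prevent this?** No. It protects concealment, meaning that nobody can foresee the next assignment. It does nothing about what the caller knows after the assignment is given.

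3. **Is that OA kept away from the family's follow-up?** No text says so. The Trial management sentence on mutual support gives permission and sets no rule. Its worked example has an OA from one team and the qualitative interviewer from another. That separates two kinds of interview; it does not separate the OA who randomised from the OA who follows up.

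4. **How easily could a different OA attend?** The staffing text lists one research assistant at each of UCL, the IoP, Cambridge and Leeds. If these four are the OAs (an assumption: implied, not stated), the planned sample gives 700 / 4 = 175 families each on average. Cambridge and Leeds would have one assessor each, so a different follow-up assessor there would have to come from another hub. Follow-up by the same person is thus likely where no rule prevents it. How often it would happen cannot be calculated.

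5. **How firm is the blinding promise?** To 18 months it is an aim, qualified by the words on feasibility in the principles of measurement. For years 2 to 5 it is unqualified. The conflict is sharpest in the later phase.

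6. **Which outcomes are exposed?**

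| Outcome | Source in the protocol | Exposure to assessor knowledge |
|---|---|---|
| Out-of-home placement (18-month primary) | Formally recorded data (Participant Adherence) | Largely protected |
| Conviction (2 to 5 year primary) | Police National Computer | Largely protected |
| K-SADS / SCID diagnoses | Diagnostic interview at later follow-up | Exposed |
| CA-SUS service use, feeding costs | Interview | Exposed |
| Family functioning, SDQ and similar scales | Completed by young person, parent or teacher | Limited; these respondents know or may know the arm whatever the OA knows |

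The diagnostic interviews fall in the phase where full blinding is promised without qualification. The cost data are collected in both phases.

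**The case against.** The strongest reply is that the protocol never says the randomising OA carries out that family's follow-up. It fixes only who telephones after baseline, and it foresees assessors covering for each other to protect blindness. No continuity of assessors into years 2 to 5 is stated either. The recruitment procedure is introduced as one possible model, still under discussion with the sites, and the blinding promise to 18 months is only an aim.

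Much of this stands and limits the point. It does not remove it: the allocation call is worded as a settled step, cross-cover is optional, and the later promise of full blinding carries no qualifier.

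A reader might infer three stronger things that the documents do not support:
- **That all 700 participants are assessed unblinded at all six follow-ups.** This would require the randomising OA to make every later visit to that family up to 48 months. The protocol does not say so, and an OA is unblinded by this route only for families he or she randomised.
- **That the primary results are compromised.** Placement and conviction are taken from records and are not rated by the OA.
- **That the coding of a young person still at home as a treatment failure would be made by someone who knows the arm.** The Measures section describes that coding but does not say who performs it.

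**Conclusion.** The point holds as a conflict between a stated procedure and the protocol's own blinding. One outcome assessor learns the arm of each family at randomisation, and nothing stops that assessor from rating the family later. The conflict is direct with the fully blind evaluations of years 2 to 5, and a tension with the qualified aim to 18 months.

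Its reach is mainly the interview-based secondary outcomes (K-SADS/SCID) and the CA-SUS service-use and cost data. Follow-up by an unblinded assessor is likely given the staffing, on the assumption that the four research assistants are the OAs. Neither its frequency nor the size or direction of any bias can be derived from the document. Because both primary outcomes are record-based, this is something that should be fixed; it does not undermine the trial's main comparison.

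**What to change.** Reconcile the recruitment, measurement, annual follow-up and trial management texts in one of two ways.

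- **Preferred: reroute the allocation.** The OA confirms to the trials unit that baseline and eligibility are complete and supplies the minimisation factors. The unit releases the allocation to the MST supervisor and the referring agency, who inform the family. The OA is not told.
- **Alternative: separate the roles.** State that an OA who has learned an allocation does no follow-up on that family.

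With either option, record any unblinding of the assessor at each follow-up, since families may still disclose their arm.

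The first option costs a change in how the randomisation service reports its result and a sentence or two in the protocol; families may hear their allocation slightly later. The second also needs only a sentence, but if Cambridge and Leeds have one assessor each, it would require cover from another hub for those families.
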